Study Document Cover Page

Official Title: : The Effects of Cardiovascular Autonomic Neuropathy (CAN) on Acute Kidney Injury and Outcome Parameters in Patients Undergoing Isolated Coronary Artery Bypass Grafting (CABG)

NCT Number:

NCT ID not yet assigned

Document Type:

Study Protocol with Statistical Analysis Plan and Informed Consent Form

Document Date:

October 1, 2020

Sponsor / Institution:

Akdeniz University Faculty of Medicine, Department of Anesthesiology and Reanimation

Principal Investigator:

[name]

Contact Information:

[contact]

Study Protocol

Title: The Effects of Cardiovascular Autonomic Neuropathy (CAN) on Acute Kidney Injury and Outcome Parameters in Patients Undergoing Isolated Coronary Artery Bypass Grafting (CABG)

Document Date: October 1, 2020

Institution: Akdeniz University Faculty of Medicine, Department of Anesthesiology and Reanimation

Principal Investigator: [name]

1. Study Objective

This study aims to analyze the effects of cardiovascular autonomic neuropathy (CAN) on primary outcome of acute kidney injury (AKI) and secondary outcome parameters in patients undergoing coronary artery bypass grafting (CABG) with extracorporeal circulation (ECC).

Specifically, the study will investigate:

The incidence of CAN in patients scheduled for isolated CABG

The effect of CAN on AKI

The impact of CAN on outcome parameters (mortality and morbidity)

The relationship between changes in regional cerebral oxygen saturation (rSO_2) and CAN

CAN Diagnosis:

1. Valsalva maneuver
2. Sitting-to-standing test
3. Temperature sensitivity test

2. Materials and Methods

This is a prospective multicenter study including all patients scheduled for CABG requiring ECC.

Preoperative CAN diagnosis will be performed 1 day before surgery using Valsalva maneuver, sitting-to-standing test, and temperature sensitivity test. A positive result in at least two tests will confirm CAN.

Preoperative data to be recorded:

Demographics and comorbidities (hypertension, diabetes, COPD, recent MI, atrial fibrillation, dyslipidemia)

Kidney function (BUN, creatinine, GFR)

Hemodynamic parameters before anesthesia induction

Baseline rSO_2 (monitoring will be blinded for clinical purposes)

Intraoperative data:

Hemodynamics, urine output, blood gases

Total cardiopulmonary bypass time, aortic cross-clamp time

Number of coronary artery anastomoses

Postoperative data:

rSO₂ at 1st and 4th hours, and 60 minutes after extubation

Intubation duration, prolonged mechanical ventilation, inotropic agent use

Renal function (BUN, creatinine, GFR) and urine output at 24, 48 hours, and 7th day per KDIGO criteria

Postoperative complications (reoperation, mediastinitis, perioperative MI, neurological complications)

Transfusion volume, IABP use, drainage volume

ICU and hospital length of stay, mortality

3. Acute Kidney Injury (KDIGO Criteria)

Stage	Serum Creatinine	Urine Output
1	1.5–1.9× baseline or >0.3 mg/dL increase	<0.5 mL/kg/hr for 6 hrs
2	2.0–2.9× baseline	<0.5 mL/kg/hr for 2 consecutive 6-hr periods
3	≥3× baseline or >4 mg/dL or RRT initiation	<0.3 mL/kg/hr for ≥24 hrs or anuria ≥12 hrs

4. Intraoperative Management

IV crystalloid infusion ≥100 mL/h from anesthesia induction

Mean arterial pressure maintained between 60–100 mmHg

If MAP <60 mmHg → 5 mg ephedrine

Inotropic agents per standard clinical practice

Transfusion if Hct <27%

Hourly urine output monitoring

ECC pump flow >1.8 L/m²/min

Body temperature during ECC ≥28°C

6. Outcomes

Intubation duration
Prolonged mechanical ventilation
Inotropic agent use
Renal failure (KDIGO criteria)
Neurological injury (stroke, confusion, agitation, memory loss, seizure, neurocognitive dysfunction)
Reoperation
Mediastinitis
Transfusion requirement
IABP use
Postoperative drainage
Perioperative MI
ICU and hospital length of stay
Mortality

7. Inclusion and Exclusion Criteria

Inclusion:

All patients >18 years old scheduled for CABG requiring ECC

Exclusion:

Emergency or revision surgeries

Orthopedic issues preventing standing test

Chronic respiratory diseases (bronchitis, asthma, COPD) affecting Valsalva reliability

Uncontrolled hypertension

Use of antiarrhythmic drugs affecting heart rate-based tests

Chronic kidney failure

Statistical Analysis Categorical variables will be presented as counts and percentages. Between-group comparisons for categorical variables will be performed using the chi-square test. The distribution of continuous variables will be evaluated using skewness and kurtosis. Variables with distribution between -1.5 and +1.5 will be considered normally distributed (parametric), otherwise non-parametric. Parametric continuous variables will be expressed as mean \pm SD. Between-group comparisons will be performed using the independent Student's t-test, and within-group temporal comparisons using the paired Student's t-test. Non-parametric continuous variables will be presented as median and interquartile range (IQR). Between-group comparisons for non-parametric variables will be performed using the Mann-Whitney U test, and within-group temporal comparisons using the Wilcoxon signed-rank test. Correlation analysis will be conducted using Pearson (parametric) or Spearman (non-parametric) correlation coefficients. Factors affecting AKI and neurological complications will be evaluated using multiple regression analysis.

Sample Size Calculation The primary objective of this study is to compare the incidence of AKI between CAN-positive and CAN-negative patients undergoing coronary artery bypass grafting (CABG). Based on previous studies using heart rate variability (HRV) for CAN diagnosis, the prevalence of CAN after myocardial infarction (MI) is approximately 60%. In the CABG population, approximately 30% of patients have diabetes and/or MI. Therefore, we anticipate a CAN prevalence of at least 20%. Postoperative AKI incidence ranges from 12–36% in the literature. Assuming that at least 20% of our patients will be CAN-positive and that AKI incidence in CAN-positive patients will be at least 10% higher than in CAN-negative patients, with $\alpha = 0.05$ and $\beta = 0.2$, a minimum of 884 patients will be required.

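### The study is multicentre and CAN is not randomised, but centre is named in neither the AKI chi-square test nor the AKI regression, so centre differences can bias the primary comparison in either direction

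*Combined protocol and SAP*

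**What the plan says.** Section 2 (Materials and Methods) sets the design: "This is a prospective multicenter study including all patients scheduled for CABG requiring ECC". The text gives no number or size of centres and no centre-level rates.

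The Sample Size Calculation section states the main comparison: "The primary objective of this study is to compare the incidence of AKI between CAN-positive and CAN-negative patients". CAN is diagnosed the day before surgery by a two-of-three test rule, so the groups are observed.

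The Statistical Analysis section gives one test for an outcome of this type: "Between-group comparisons for categorical variables will be performed using the chi-square test". Its only adjusted analysis is one sentence: "Factors affecting AKI and neurological complications will be evaluated using multiple regression analysis". No covariates are listed, and this regression is not called the primary analysis. Neither the analysis nor the sample size contains a centre stratum, covariate, random effect or clustering allowance.

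The planning assumptions are "Assuming that at least 20% of our patients will be CAN-positive" and "AKI incidence in CAN-positive patients will be at least 10% higher than in CAN-negative patients". For background, "Postoperative AKI incidence ranges from 12–36% in the literature".

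**The concern.** In a randomised trial stratified by centre, the groups would be balanced within centres by design. Here nothing balances them. Centre confounds the pooled 2×2 table if it is related to both CAN status and AKI, and the protocol leaves both routes open.

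- **CAN.** Section 2 gives the two-of-three rule but no cut-off for a positive result on any of the three tests, so centres could classify similar patients differently. Case mix may differ as well.
- **AKI.** Some care is left to local practice (section 4: "Inotropic agents per standard clinical practice"), and other items are set only as lower limits.

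If the centres with more CAN also have more AKI, the chi-square can show a difference that exists in no centre. If they have less AKI, it can shrink a real one. Centre is known for every patient, so this source of bias can be removed in the analysis.

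**Working it through.** **1. The plan's own figure.** Inputs from the Sample Size Calculation section: CAN prevalence 20% (1:4), difference 10% read as percentage points, α = 0.05, power 80%. The CAN-negative AKI rate is not stated. I assume 20%, hence 30% in CAN-positive patients, and a two-sided test. The pooled rate is (0.30 + 4×0.20)/5 = 0.22.

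n(CAN-positive) = [1.96√(0.22×0.78×1.25) + 0.842√(0.30×0.70 + 0.20×0.80/4)]² / 0.10² = 176.5, rounded up to 177.

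n(CAN-negative) = 4 × 176.505 = 706.02, rounded up to 707. The total is 884, as stated. The calculation has no term for centre.

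**2. Size of the bias.** Let two centres have shares w₁ and w₂, CAN prevalences c₁ and c₂, and AKI rates p₁ and p₂ that do not depend on CAN. With overall prevalence c̄, the pooled difference is

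w₁w₂(c₂ − c₁)(p₂ − p₁) / [c̄(1 − c̄)].

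For equal centres and c̄ = 0.20 the divisor is 4 × 0.16 = 0.64, so the bias is (CAN gap × AKI gap)/0.64. All centre-level rates below are assumptions. The 12% and 36% are the ends of the literature range for AKI, used only as outer limits.

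For the widest case in full:
- CAN-positive: (0.10×0.12 + 0.30×0.36)/0.40 = 30.0%
- CAN-negative: (0.90×0.12 + 0.70×0.36)/1.60 = 22.5%

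The spurious difference is 7.5 points. At 177 v 707 the pooled standard error is √[0.24×0.76×(1/177 + 1/707)] = 3.59 points, so significance needs 1.96 × 3.59 = 7.04 points. The unpooled standard error is √(0.30×0.70/177 + 0.225×0.775/707) = 3.79 points. The chance of exceeding 7.04 is Φ[(7.5 − 7.04)/3.79], about 55%.

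The same steps give the table below. The last two columns assume a true 10-point difference with the CAN rates of the two centres swapped.

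| AKI by centre | CAN by centre | Bias, no true effect | False positives | True 10 points appears as | Power |
|---|---|---|---|---|---|
| 20% / 28% | 18% / 22% | 0.04×0.08/0.64 = 0.5 | 5% | 9.5 | 72% |
| 18% / 30% | 15% / 25% | 0.10×0.12/0.64 = 1.9 | 9% | 8.1 | 59% |
| 12% / 36% | 15% / 25% | 0.10×0.24/0.64 = 3.75 | 19% | 6.25 | 40% |
| 12% / 36% | 10% / 30% | 0.20×0.24/0.64 = 7.5 | 55% | 2.5 | 10% |

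Without confounding, the crude test has about 76% power at these average AKI rates. The 80% belongs to a CAN-negative rate of 20%.

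**3. What makes it smaller.**
- If either rate is equal across centres, one gap is 0 and so is the bias.
- With a 90:10 split, widest rates, and the large centre having the lower rates: c̄ = 0.12 and the bias is 0.09×0.20×0.24/(0.12×0.88) = 4.1 points. If the large centre has the higher rates: c̄ = 0.28 and the bias is 0.00432/(0.28×0.72) = 2.1 points.
- Five equal centres evenly spread over AKI 12–36% and CAN 10–30%, perfectly aligned: covariance 2×(0.10×0.12 + 0.05×0.06)/5 = 0.006, and 0.006/0.16 = 3.75 points.
- With two equal centres at the full 12–36% spread, a bias above 5 points needs a CAN gap of 0.05×0.64/0.24 = 13.3 points, roughly 13% v 27%.

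**4. After stratification.** A Cochran-Mantel-Haenszel (CMH) test was simulated 40,000 times per setting, at N = 884 with two equal centres. AKI rates were 12/36%, 18/30% or 20/20%. CAN rates were 20/20%, 15/25%, 10/30% or 30/10%. The Mantel-Haenszel risk difference returned the true value (0 or 10 points) in every setting. Two-sided type I error was about 5%. Power for 10 points was 72% to 81%, against 76% to 80% for the crude test when centre does not confound.

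**The case against.** The strongest reply is that the size is hypothetical. A reader might infer that centre differences could create or hide most of the 10-point difference sought. The documents do not support that. The 12–36% is a range across published studies, not between centres of this study, and no spread in CAN prevalence is given. Only the widest of the four scenarios exceeds half of 10 points. It needs two equal centres, the full AKI range and a wide CAN gap together, and the mildest scenario leaves the false-positive rate essentially nominal. This part of the objection stands.

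Second, the protocol does standardise a good deal. Section 4 sets common rules for fluids, arterial pressure, transfusion, pump flow, temperature and urine monitoring. Section 3 applies one KDIGO table. Section 7 excludes emergency and revision surgery and chronic kidney failure, which narrows case mix. These rules make a 24-point gap in AKI between centres less likely, but do not rule out smaller gaps.

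Third, the chi-square is not the only AKI analysis. A reader who took the plan to have no adjusted analysis would be wrong, because a multiple regression for AKI is planned. It does not answer the point as written: it names neither centre nor any other covariate, and nothing makes it the basis for the primary conclusion.

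Fourth, stratifying by centre leaves confounding within centres by factors such as diabetes or recent MI. The sample size text itself ties expected CAN prevalence to diabetes and MI. That is correct. It is a reason to specify the regression as well, not to leave centre out.

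**Conclusion.** The point holds as a defect of moderate and uncertain size. Three facts are in the text: the study is multicentre, the exposure is observed, and centre enters neither the stated AKI comparison nor the regression. It follows that the primary comparison is open to bias by centre, upward or downward.

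The magnitude rests wholly on assumed centre rates and sizes. Under those assumptions it runs from under 1 point to 7.5 points, and the top figure should be read as an extreme case. Moderate spreads, giving roughly 2 to 4 points, are enough to double or nearly quadruple the nominal 5% error rate, or to take power well below the planned 80%. The sample size of 884 reproduces and is not itself faulted here.

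**What to change.** Amend the Statistical Analysis section before AKI is compared by CAN group:

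- Make the primary AKI comparison centre-stratified: a Cochran-Mantel-Haenszel test with a common risk difference or odds ratio and its 95% confidence interval. The risk difference matches the 10-point planning assumption. An equivalent centre-adjusted model would also serve, if named as primary.
- Include CAN and centre as terms in the planned AKI regression, together with pre-specified patient factors such as diabetes and recent MI, to deal with confounding within centres.
- Fix in advance a rule for merging very small centres.
- Report the number of centres, with patients, CAN prevalence and AKI rate for each, so that readers can judge how much centre mattered.

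The cost is SAP wording and a little more analysis. No new data are needed beyond the centre identifier. Power may fall slightly: in the simulations it was 72% to 81% at N = 884, and the low end arose when CAN prevalence differed widely between centres (10% v 30%).

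### The preoperative record holds only recent MI and nothing on ventricular function, so with the data as listed the AKI regression cannot adjust for older infarction or ventricular dysfunction.

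*Combined protocol and SAP*

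**What the plan says.** The preoperative list in section 2 (Materials and Methods) gives the history items as "Demographics and comorbidities (hypertension, diabetes, COPD, recent MI, atrial fibrillation, dyslipidemia". The list is closed: nothing marks the six conditions as examples. The word recent is not defined. The other preoperative items are kidney function, baseline rSO2 and "Hemodynamic parameters before anesthesia induction", with no echocardiographic or other measure of ventricular function named.

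Section 7 admits "All patients >18 years old scheduled for CABG requiring ECC", and none of its exclusions concerns earlier infarction, heart failure or low ejection fraction.

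The sample size section states the primary aim as to "compare the incidence of AKI between CAN-positive and CAN-negative patients". To justify the expected CAN prevalence, it says that in studies using heart rate variability "the prevalence of CAN after myocardial infarction (MI) is approximately 60" per cent, and that in CABG "approximately 30% of patients have diabetes and/or MI". It then assumes that "at least 20% of our patients will be CAN-positive".

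The only adjustment described is one sentence in the statistical analysis section: "Factors affecting AKI and neurological complications will be evaluated using multiple regression analysis". It gives no covariate list and does not name CAN as a term.

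**The concern.** Section 1 asks about the effect of CAN on AKI, but patients arrive with or without CAN. Anything that makes CAN more likely and also raises AKI risk will appear as a CAN effect unless it is measured and adjusted for.

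The plan itself treats infarction as a strong correlate of CAN, without limiting it to recent events, yet collects only the recent part. Ventricular dysfunction is a second candidate. On clinical reasoning it could alter the Valsalva and standing responses and also reduce renal perfusion around bypass. Neither older MI nor ventricular function is on the list, so a regression run on the listed data cannot include them. At stake is whether a positive primary result can be read as an effect of CAN rather than of the heart disease that accompanies it.

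**Working it through.** **The plan's own figure.** The CAN-negative AKI rate is not stated. Taking 20% (an assumption inside the quoted 12–36%) against 30%, with 1:4 allocation, two-sided alpha 0.05, 80% power, pooled variance and no continuity correction, the formula gives 176.5 CAN-positive and 4 × 176.5 = 706.0 CAN-negative. Rounding each up gives 177 + 707 = 884, the stated minimum. Other combinations also come within 3% of it, so 20% is a workable base rate, not one the plan identifies. This point does not change 884.

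**Inputs for the bias.** From the plan: 60% CAN after MI, at least 20% CAN overall, N = 884. Assumed: old MI in 10–15% of patients, CAN after old MI in 40–60%, CAN overall in 20–30%, an AKI excess of 5–10 percentage points with old MI, AKI of 20% in the CAN-negative group, and no true CAN effect.

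**Formulas.** Let m be the share with old MI, c the CAN rate among them, and k the overall CAN rate.
- Old MI among CAN-positive: c × m / k
- Old MI among CAN-negative: (1 − c) × m / (1 − k)
- Spurious AKI difference: (first share − second share) × AKI excess

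For m = 15%, c = 60%, k = 20%: 0.60 × 0.15 / 0.20 = 45% and 0.40 × 0.15 / 0.80 = 7.5%. The gap is 37.5 points. Multiplying by 0.05 and 0.10 gives 1.9 and 3.75 points.

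**False-positive rate.** Take 3.75 points: AKI of 23.75% in 177 against 20% in 707. The pooled rate is (177 × 0.2375 + 707 × 0.20) / 884 = 0.2075. The null standard error is √(0.2075 × 0.7925 × (1/177 + 1/707)) = 0.0341, and the unpooled one is √(0.2375 × 0.7625/177 + 0.16/707) = 0.0353. The upper-tail probability is Φ((0.0375 − 1.96 × 0.0341)/0.0353) = Φ(−0.83) = 20.4%. The lower tail adds about 0.2%, giving 20.5% after rounding.

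The other cases are computed the same way, with groups of 265 and 619 when CAN is 30%:

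| CAN overall | Old MI | CAN after old MI | Old MI in CAN+ / CAN− | Spurious difference (points) | Rejection of a true null |
|---|---|---|---|---|---|
| 20% | 15% | 60% | 45% / 7.5% | 1.9–3.75 | 9.1–20.5% |
| 20% | 10% | 60% | 30% / 5% | 1.25–2.5 | 6.9–12.1% |
| 30% | 15% | 60% | 30% / 8.6% | 1.1–2.1 | 6.7–11.5% |
| 20% | 15% | 40% | 30% / 11.25% | 0.9–1.9 | 6.1–9.1% |
| 20% | 10% | 40% | 20% / 7.5% | 0.6–1.25 | 5.6–6.9% |
| 30% | 10% | 40% | 13.3% / 8.6% | 0.2–0.5 | 5.1–5.4% |

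The last row puts all three low inputs together and is the floor of the assumed ranges. With no bias the rate is 5%. These are crude differences, before any adjustment for recorded covariates. No comparable calculation is offered for ejection fraction or heart failure, because the documents give no figure to start from.

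**The case against.** The factual gap is hard to dispute. The objections concern how far it reaches.

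- A reader might infer that the confounding can never be removed. The documents do not support that. If the cardiac work-up exists in the patient's records, MI history and ejection fraction could be retrieved later. What stands is that the plan makes no provision for it.
- A reader might infer that the plan makes MI the main source of CAN. It does not. The 60% is a prevalence within a subgroup, not a share of CAN cases, and the 30% pools diabetes with MI without ranking them. Diabetes is recorded.
- The 60% comes from HRV-based studies with no stated time since infarction. This study labels CAN by at least two positive results among the Valsalva, sit-to-stand and temperature tests. Applying 60% to old MI is therefore an inference, which is why 40% is also shown.
- Recent MI, diabetes, atrial fibrillation and baseline GFR are recorded and would absorb part of the bias. This stands: the bias left after adjustment should be smaller than the crude figures, by an unknown amount. Inotrope and IABP use cannot fill the gap, because both are recorded after surgery and are listed outcomes in section 6.
- It is tempting to say that a patient with an old infarct will be stored as having no MI. The case-report form is not among the documents. What can be said is that recent is undefined and no item covers older events.

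**Conclusion.** The point holds as a gap in planned data collection. With the listed data, the AKI regression cannot adjust for older MI or ventricular dysfunction, so part of any CAN–AKI association may be confounding.

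Its importance is not established. For old MI, the crude bias is about 0.6 to 3.8 points, with a false-positive rate of about 6% to 20%, in all but the last case worked. That last case, with every low input combined, gives as little as 0.2 points and about 5%. The top of the range is 3.75/10 = 37.5% of the effect sought and needs every high input at once. Old-MI prevalence and its AKI excess are assumptions, and the upward direction depends on old MI raising AKI. The ventricular-function pathway is clinical reasoning only.

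A reader might conclude that a positive CAN result would be an artefact. The documents do not support that. They support only that the plan, as written, could not separate the two explanations. This is a cheap improvement worth making, not a flaw that invalidates the design.

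**What to change.** In the preoperative list, replace the recent-MI item with *any prior MI (date of last event)*. Add heart failure history and preoperative ejection fraction, where available from the existing cardiac work-up. State in the statistical analysis section that the AKI regression contains CAN together with these items and diabetes, and say how missing values will be handled.

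The cost is three case-report-form fields and some missing ejection fractions. The model has room: at the planned rates about 177 × 0.30 + 707 × 0.20 = 194 AKI events are expected, so a few extra degrees of freedom are affordable.

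There is also some loss of precision for the CAN effect, because the new covariates correlate with CAN. For infarction alone, with 60% CAN after MI and 20% overall, the correlation is (0.06 − 0.02)/√(0.10 × 0.90 × 0.20 × 0.80) = 0.33 if 10% have an old MI, and (0.09 − 0.03)/√(0.15 × 0.85 × 0.20 × 0.80) = 0.42 if 15% do. By the approximation N/(1 − R²), keeping the same power for the adjusted comparison would take 884 to about 995 or 1,073. Those figures depend on the 60% and shrink if CAN after old MI is less common. If enrolment is not extended, the sponsor should expect a somewhat wider interval in exchange for a less confounded estimate.

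### ICU stay, hospital stay and intubation duration are compared with no rule for deaths; if deaths are unequal and mainly early, the stay comparisons lean towards the group with more deaths

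*Combined protocol and SAP*

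**What the plan says.** Section 2 (Materials and Methods, postoperative data) lists "Intubation duration, prolonged mechanical ventilation, inotropic agent use" and, further down, "ICU and hospital length of stay, mortality". Section 6 (Outcomes) names the durations again, with mortality as its own entry.

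The Statistical Analysis section gives two between-group tests for continuous variables, chosen by skewness and kurtosis. For those judged normal: "Between-group comparisons will be performed using the independent Student's t-test". For the rest: "Between-group comparisons for non-parametric variables will be performed using the Mann-Whitney U test". Modelling is limited to two other endpoints: "Factors affecting AKI and neurological complications will be evaluated using multiple regression analysis".

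Nothing says how a patient who dies in the ICU, in hospital or while intubated enters the duration comparisons. There is no worst rank, no count of days alive and free of the event, no time-to-event analysis and no restriction to survivors.

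**The concern.** A length of stay can end in discharge or in death. A plain t-test or rank test sees only the number of days. A patient who dies on day 2 and one who goes home unusually fast both count as short, favourable values.

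Mortality is itself one of the outcomes on which section 1 asks about an effect of CAN, so unequal deaths are a scenario that the study sets out to examine. If deaths were more frequent among CAN-positive patients and came early, they would pull that group's stay down and mask some of any true prolongation. Showing mortality in another row of the table does not correct the p-value for stay.

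**Working it through.** **Group sizes.** The plan's only relevant figure is its total of 884. With AKI of 20% v 30% (the 20% base is an assumption inside the plan's 12–36% range), a 1:4 split, two-sided 0.05 (sidedness is not stated), 80% power and pooled variance:

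- pooled proportion = (0.30 + 4 × 0.20)/5 = 0.22
- n(CAN+) = [1.960 × √(1.25 × 0.22 × 0.78) + 0.842 × √(0.30 × 0.70 + 0.20 × 0.80/4)]² / 0.10² = 176.5, so 177
- total = 5 × 177 = 885, against 884 stated

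The total reproduces. The split follows from "Assuming that at least 20% of our patients will be CAN-positive": 0.20 × 884 = 176.8, so 177 v 707.

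**Assumed inputs.** The documents give no mortality or stay figures. Let p1 and p0 be mortality in CAN-positive and CAN-negative patients, and let survivors' stays have the same distribution in both groups. An undistorted stay comparison then has z = 0.

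**Null standard error** of P(CAN+ stay > CAN− stay): √[885/(12 × 177 × 707)] = 0.0243.

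**Raw stays, deaths spread evenly over the lowest 10% of stays.** A death exceeds a survivor's stay with probability 0.05, and a survivor's stay exceeds a death with probability 0.95. Like pairs contribute 0.5. Hence P − 0.5 = −0.45 × (p1 − p0).

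**Deaths tied at the worst rank.** P − 0.5 = +0.50 × (p1 − p0).

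| Mortality | Raw z | Worst-rank z |
|---|---|---|
| 3% v 2% | −0.0045/0.0243 = −0.19 | +0.0050/0.0243 = +0.21 |
| 5% v 2% | −0.0135/0.0243 = −0.56 | +0.0150/0.0243 = +0.62 |
| 8% v 2% | −0.0270/0.0243 = −1.11 | +0.0300/0.0243 = +1.23 |

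The distortion of the stay comparison is the raw column, measured from zero.

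**Timing of death, at 5% v 2%.** Deaths in the lowest 10% of stays give z = −0.56. Deaths spread over the whole range give 0.00. Deaths in the top 10% give +0.56.

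**Simulation on the day scale.** Assumptions: 177 v 707, log-normal stay with median 7 days and log-SD 0.5, early deaths uniform over days 0–3, late deaths around a median of 14 days, 1,500 runs per scenario.

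- No true difference, all deaths early: the raw mean difference (CAN+ minus CAN−) is −0.13, −0.27 and −0.46 days at mortality 4% v 2%, 6% v 2% and 10% v 3%. The raw Mann-Whitney test declares CAN-positive stays shorter in 5%, 13% and 31% of runs (nominal 2.5%).
- No true difference, all deaths late: +0.18 to +0.62 days over the same pairs. Half early and half late: 0.01 to 0.08 days.
- True stay 15% longer in CAN-positive patients: the raw test detects it in 90% of runs with no deaths (3,000 runs), 88% at 2% v 2% early, 76% at 4% v 2% early and 59% at 6% v 2% early. At 6% v 2% it detects it in 80% with mixed timing and 94% with late deaths.
- In that setting at 6% v 2% early, worst ranking gives 96%. Part of that is the mortality difference itself, so the loss due to raw scoring is better read as 90% to 59%.

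**The case against.** Several points stand against a stronger reading.

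- **Expected direction.** A reader might infer that the study expects more deaths with CAN. The documents do not say so. Section 1 asks about mortality without a direction, and the only stated expectation concerns the primary outcome: "AKI incidence in CAN-positive patients will be at least 10% higher than in CAN-negative patients".
- **An unconditional lean.** A reader might infer that the comparison always favours the group with more deaths. It does so only if deaths are mainly early. Spread deaths cancel, and late deaths lengthen that group's stay.
- **Size.** The gap between the raw and worst-rank z values is 1.2 standard errors at 5% v 2% (0.56 + 0.62) and 2.3 at 8% v 2% (1.11 + 1.23). It is tempting to call all of this bias. About half is the mortality difference that worst ranking adds, which changes the question and does not correct an error.
- **Intubation duration.** A patient who dies while intubated contributes the time to death. That is a low value only if death comes before most patients are extubated. This was not worked out separately.
- **Deaths remain visible.** Mortality is compared in its own right. With 177 v 707, the pooled two-proportion z is 0.8 at 3% v 2%, 2.2 at 5% v 2% and 4.1 at 8% v 2%, so a large distortion would usually sit beside a visible excess of deaths.
- **Silence.** That durations are tested as recorded is inferred from the generic tests and the absence of a rule. A survivors-only analysis is not excluded.

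These points limit the concern but do not remove it. A visible mortality row does not repair the stay p-value. The silence leaves the handling of deaths open to choice after the data are seen, and a survivors-only analysis would have a selection problem of its own.

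**Conclusion.** The concern holds in a conditional form. The plan's only analysis of these three durations does not distinguish discharge or extubation from death, so a duration cut short by death is read as a good outcome. With unequal and mainly early deaths, the stay comparisons are distorted towards the group with more deaths by about 0.2, 0.55 or 1.1 standard errors at assumed mortality of 3%, 5% or 8% v 2%. On their own, none of these shifts reaches significance. The distortion disappears if deaths are spread across stays and reverses if they are late. A claim that the analysis will reverse the sign of a CAN effect is not supported, and no direction is established for intubation duration.

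Every mortality and stay figure here is an assumption. These are secondary outcomes and the AKI comparison is unaffected. This is a cheap improvement worth making before analysis.

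**What to change.** Add to the Statistical Analysis section: ICU stay, hospital stay and intubation duration will be compared between CAN groups by the Mann-Whitney test, with all in-hospital deaths tied at the worst rank; medians (IQR) among survivors and the number of deaths will be reported for each group. For these three variables this replaces the choice of test by skewness and kurtosis.

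The cost is SAP wording only. No extra patients are needed, and death is already recorded. The downside is that the p-value then reflects death and duration together, so the survivor medians and death counts must stand beside it.

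An acceptable alternative is to analyse time to discharge or extubation with death as a competing event. Whichever is chosen should be fixed before the outcome data are examined.
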